6.4.4 Subgroup analysis

A summary table (number and percentage of patients) of the following groups will be created by treatment group:

- Patients with ILD per MH (defined with PTs: interstitial lung disease and pulmonary fibrosis) by treatment group (already listed as subgroup analysis in [section 6.2.5](#))
- Patients with ILD confirmed by HRCT (confirmed, if interstitial fibrosis and /or ground glass found on HRCT) divided to sub-categories:
 - All patients with ILD per HRCT
 - All patients with ILD per HRCT done pre-therapy (HRCT prior randomization)
 - All patients with ILD per HRCT done post-baseline (HRCT after randomization)
- Patients with ILD per MH and confirmed by HRCT (if a patient with ILD in MH has HRCT done pre-randomization with interstitial fibrosis and/or ground glass found)
- Patients with worsening or new onset of ILD per AE (defined with PTs interstitial lung disease and pulmonary fibrosis in AE data)
- Patients with worsening or new onset of ILD (defined with PTs interstitial lung disease and pulmonary fibrosis in AE data) confirmed by HRCT (Worsening is confirmed, when interstitial fibrosis and/or ground glass finding is defined as worsened on HRCT. New onset is confirmed, when interstitial fibrosis and/or ground glass found on HCRT. HRCT confirms AE in question, if it has been done 28 days before – 28 days after AE start date and fulfills the requirements defined before.)

Descriptive analyses by ILD (yes/no) per MH will be performed as follows:

- TEAEs by treatment group
- TESAEs by treatment group
- Lung function tests (FVC%, FVC, DLco% predicted, DLco (mmol/min/kPa),) by treatment group
- Discontinuations of study medication by treatment group

Obligatory HRCTs were performed at baseline or during the study to be able to confirm possible ILD finding in MH or AE.

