6.1.2 Medical history and concomitant medication

Medical history (MH) and concomitant medication (CM) will be summarized by treatment group and overall.

Medical history findings will be coded by Medical Dictionary for Regulatory Activities (MedDRA) codes. System organ class (SOC) and preferred term (PT) will be used in tabulations.

Medical history findings (i.e., previous diagnoses, diseases or surgeries) meeting all criteria listed below will be collected:

- Pertaining to the study indication
- Started before signing of the informed consent
- Considered relevant to the study
- Medical history related to concomitant therapy

In the following differentiation between medical history and AEs, the term “condition” may include abnormal e.g., physical examination findings, symptoms, diseases, laboratory, ECG.

- Conditions that started before signing of informed consent and for which no symptoms or treatment are present until signing of informed consent are recorded as medical history (e.g., seasonal allergy without acute complaints).
- Conditions that started before signing of informed consent and for which symptoms or treatment are present after signing of informed consent, at unchanged intensity, are recorded as medical history (e.g., allergic pollinosis).
- Conditions that started or deteriorated after signing of informed consent will be documented as AEs.

Prior and concomitant medications will be coded by Anatomical Therapeutic Chemical (ATC) classification system according to the World Health Organization Drug Dictionary (WHO-DD). The ATC class is taken from the WHO-DD code (first character) and the ATC subclass is taken from the WHO-DD code (first 3 characters).

Bayer Drug Groupings (BDG) will be used to select concomitant medications of special interest. The selected concomitant medications will be summarized by parent BDG, BDG and substance name. See the [main SAP section 6.1.2](#) for reference.

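### SAP 6.4.4 can count unchanged, pre-existing ILD as HRCT-confirmed once an ILD adverse event is reported, because its new-onset test asks only whether ILD is present on the scan

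*SAP*

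**What the plan says.** SAP 6.4.4 plans a table of patient counts by treatment group for several ILD categories. One row is "Patients with worsening or new onset of ILD (defined with PTs interstitial lung disease and pulmonary fibrosis in AE data) confirmed by HRCT". A patient enters it in two steps. First, an adverse event must be coded to one of the two preferred terms. Second, an HRCT must support the event, which it can do only "if it has been done 28 days before – 28 days after AE start date" and if it meets one of two tests:

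- Worsening: "Worsening is confirmed, when interstitial fibrosis and/or ground glass finding is defined as worsened on HRCT".
- New onset: "New onset is confirmed, when interstitial fibrosis and/or ground glass found on HCRT".

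The same table has separate rows for ILD in medical history, for ILD adverse events without HRCT confirmation, and for "All patients with ILD per HRCT done pre-therapy (HRCT prior randomization").

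On the availability of scans the section says "Obligatory HRCTs were performed at baseline or during the study to be able to confirm possible ILD finding in MH or AE".

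**The concern.** The two tests are not of the same kind. The worsening test compares a scan with something earlier. The new-onset test does not: it is the criterion the table uses elsewhere to say that a patient has ILD at all. One scan can show that ILD exists, but not when it began.

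A patient whose ILD was already there and has not changed is neither a worsening nor a new-onset case, yet can pass the second test and be shown as confirmed.

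This matters because SAP section 2 gives continued exploratory benefit-risk assessment as the purpose of the extension evaluation, and everyone in the extension takes riociguat, so there is no concurrent placebo group against which to judge the count. Protocol section 1.3 records a potential safety issue with riociguat in pulmonary hypertension associated with idiopathic interstitial pneumonias. The extension has no data monitoring committee (SAP 4.4). A row labelled as HRCT-confirmed will carry weight with readers.

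**Working it through.** The documents give no figure to reproduce here, so the check is a reading of the rule and a test of it case by case.

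**Inputs**

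- The two confirmation tests, the time window and the pooled row: SAP 6.4.4.
- What becomes an adverse event: "Conditions that started or deteriorated after signing of informed consent will be documented as AEs" (SAP 6.1.2). Known conditions "for which symptoms or treatment are present after signing of informed consent, at unchanged intensity, are recorded as medical history".
- Scope of the safety data: SAP 6.4 also includes events that began in the main phase and continued into the extension.
- Availability of an earlier scan: SAP 6.4.4 allows the HRCT to be at baseline or later, and the schedule of evaluations (Protocol Table 7-1) has no HRCT line. A baseline scan is therefore not guaranteed.

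**The rule applied to six patients**

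| Case | ILD adverse event | Earlier evidence | In-window HRCT | Result under SAP 6.4.4 | Correct? |
|---|---|---|---|---|---|
| A | None | Any | Any | Not counted | Yes |
| B | Yes | No history, no earlier HRCT | ILD present | Confirmed as new onset | Cannot be verified |
| C | Yes | No history, earlier HRCT showed ILD | Present, unchanged | Confirmed as new onset | No |
| D | Yes | ILD in medical history | Present, unchanged | Fails the worsened test, passes the presence test as literally worded | No, if counted |
| E | Yes | Earlier HRCT clear | ILD present | Confirmed as new onset | Yes |
| F | Yes | Earlier HRCT showed ILD | Worsened | Confirmed | Yes |

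Case C can sit in the pre-therapy ILD row and in the confirmed row of the same table. Case D arises because the SAP does not say how an event is assigned to worsening or to new onset. Without that assignment, a scan that fails the stricter test can be accepted under the looser one.

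**Timing.** The window covers 28 + 1 + 28 = 57 calendar days. For an event starting within 28 days after the first riociguat dose, the confirming scan may pre-date that dose.

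**Comparison with the protocol.** Step 1 of the CRISS algorithm (Protocol 8.4.2.2) makes its HRCT requirement depend on whether a previous HRCT had already shown ILD. Reference to earlier imaging is thus already part of this trial's definitions, but it is absent from SAP 6.4.4.

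**The case against.** The strongest reply is that newness comes from the adverse event report, not from the scan. An event is by definition something that began or deteriorated after consent, and known stable ILD belongs in medical history. The HRCT then only supports the diagnosis. This stands in part: it means pre-existing ILD *can* be confirmed, not that it routinely *is*. It does not remove the problem. The table already has a row for ILD by adverse event alone, so the HRCT row adds value only if it checks that report, and on onset it cannot. ILD first noticed on a study scan may be reported as an event although it began earlier.

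The second reply is that the row pools worsening and new onset, so a patient whose prior ILD truly worsened is counted correctly whichever label applies. That is right (case F), and it limits the error to unchanged disease (cases C and D) and unverifiable onset (case B).

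A reader might infer four stronger things that the documents do not support:

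- *That a published new-onset count is inflated.* No separate new-onset count is planned.
- *That the events arose on riociguat.* The row draws on adverse event data without limiting it to treatment-emergent events, and SAP 6.4 includes main-phase events that continue. An event in a patient first randomized to placebo may have begun on placebo.
- *That the row as a whole is biased upward.* Unchanged prior ILD can only add cases, but genuine events with no scan in the window drop out. The net direction is not known.
- *That a multiplier can be attached.* Suppose 20% of patients without ILD in their history already have it on CT, and 2% of the others have true new onset. If 10% of the first group report an event, the result is 0.20 × 0.10 + 0.80 × 0.02 = 3.6% against a true 0.80 × 0.02 = 1.6%, a ratio of 2.25. With a 2% event rate in both groups it is 0.20 × 0.02 + 0.80 × 0.02 = 2.0% against 1.6%, a ratio of 1.25. None of these inputs is in the documents. Both calculations also treat every event in patients with prior findings as false and assume that each has an in-window scan.

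Finally, the importance should not be overstated. The tabulations are descriptive, and ILD is not among the adverse events of special interest (Protocol 7.5.1.6). Amendment 6 responded to palpitations and dizziness in patients with ILD, not to ILD onset.

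**Conclusion.** The concern holds in a limited form. As written, the rule lets ILD that pre-dated treatment and has not changed be counted as HRCT-confirmed worsening or new onset, provided an ILD or pulmonary fibrosis event has been reported and a scan in the window shows the disease. The worsened test can be bypassed because no assignment rule separates the two limbs. Descriptive status does not cure this, since the row is labelled as confirmed and serves a benefit-risk assessment.

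The size cannot be derived from the documents. It depends on how many extension patients had unrecognized or unchanged ILD, how often that was reported as an event, and how many had a scan in the window. No claim about riociguat causing the events, or about the net bias of the row, follows. The main-phase SAP (version 4.0), to which this SAP refers, is not among the documents, so any HRCT reading rule there could not be checked. The defect is worth correcting because the remedy is cheap. It touches no confirmatory result.

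**What to change.** Amend SAP 6.4.4 as follows:

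1. Confirm new onset only if medical history has no ILD term, the most recent HRCT before the in-window scan shows neither fibrosis nor ground glass, and the in-window scan shows at least one of them.
2. If medical history or an earlier HRCT already shows ILD, confirm the event only under the worsened test.
3. Put events with no earlier HRCT in a separate row, for example *ILD on HRCT, onset not established*.
4. Show worsening and new onset as separate counts, so that the assignment of each event is visible.

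The cost is a few lines of SAP text and extra table rows, using scans already collected. The downside is that some events will move to the undetermined row because a baseline HRCT is not guaranteed for every patient. If many do, that is an honest statement of what the imaging can show.

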6.4.5 Possible changes of observations in main phase

If there are corrected observations in AE, MH or CM domains after analysis of main treatment phase, those will be listed per domain by subject.

7. Document history and changes in the planned statistical analysis

- Approval of the SAP version 4.0 dated 22 Dec 2017.
- Approval of the SAP for Benefit-risk update version 1.0 dated 12 Jul 2018.

8. References

1. SF-36v2® Advanced Scoring Guidelines:
How to submit data, what you will receive back, and scoring timeline Final.
Revised: VL, KM, MW, AY, 11/13/2014
2. IMACS Form 04a: Instructions for the Health Assessment Questionnaire
